## 9.3

## Interim Reports for the Data and Safety Monitoring Board

These are prepared by study staff in advance of each meeting.

## 9.4

## Efficacy Analyses

Efficacy analyses will be based on comparisons between the Med-South dietary pattern intervention to WW with respect to efficacy endpoints.

### 9.4.1

### Primary Efficacy Analyses

The primary analyses will be conducted using the ITT Population (i.e., all randomized participants) and will be repeated secondarily using the Per Protocol Population. We will compare the longitudinal mean % change in body weight between groups using analysis of covariance (ANCOVA), conducted using a linear mixed model. A mixed model will allow for the inclusion of all observed follow-up data for all participants. The model will include fixed effects for group, follow-up visit (4, 12, or 24 months), group-by-visit interactions, site (see operational definition as below), baseline weight, race/ethnicity, gender, and diabetes status. (When reviewing the analysis in May, 2025, we realize we inadvertently did not include age in the model. Our final models included age.) There is no plan to include other baseline variables (including those different) in the model. To account for within-participant correlation, the model will allow for correlated error terms using an unstructured covariance matrix. For the primary comparison, we will use a linear contrast (i.e., group -1 1 group\*follow-up visit 0 0 -1 0 0 1) of the model parameters to test for a treatment effect at 24-months at the 5% significance level. Secondarily, we will compare the groups at other time points and will estimate effect sizes along with 95% confidence intervals for each comparison. Additionally, we will expand the model by including appropriate interaction terms, one at a time, to examine the potential heterogeneity of intervention effect in sub-groups, including diagnosis (diabetes vs. no diabetes), race/ethnicity, sex (for gender, 2 participants not binary, so will for these will use sex as captured in the electronic health record), and by degree of baseline obesity ( $BMI \geq \text{median}$  vs. less). Interaction terms will be tested at the 5% significance level.

Next, we will use a longitudinal mixed effects logistic regression model to compare the groups for proportions losing  $\geq 5\%$  baseline body weight at each follow-up visit. Estimates of odds ratios and 95% confidence intervals will be provided. This model will control for the same covariates specified for the primary model and test the same interaction terms.

**Study sites:** Wave 3: Durham family medicine: 17, Durham family medicine at Southpoint 9: total 26. North Chatham internal medicine and pediatrics 27. Will combine the 2 Durham family medicine sites as they are physically located close to one another and are our 2 Durham practices.

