4.3 JUSTIFICATION FOR INTERVENTION

We propose individual counseling for the Med-South Weight Loss Group. Delivery by individual contacts (without group-based format as an option) is an adaptation based on: 1) contextual factors (e.g., poor patient uptake of group programs, time needed to train and supervise group facilitators, and logistical challenges) that could negatively impact group-based delivery in primary care settings,⁷⁹ and 2) advantages of individual contacts and evidence of comparable weight loss outcomes in group vs. individual treatment delivery.^{3,80} With this change, intervention delivery is made easier for staff in primary care settings, provides the advantage of a closer relationship between participant and interventionist, and allows tailoring of the intervention to fit the needs of individual participants. Participants who receive the WW™ intervention may attend group session (workshops) or use the WW™ digital interface for web and/or smart phones.

The number of contacts are similar to what we have used in prior weight loss studies^{75, 81, 82} and consistent with the notion that successful weight loss programs require an intensive intervention.

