6.1.2 ADMINISTRATION AND/OR DOSING

Logistics of giving the Med-South Weight Loss Program

- The intervention will be given by trained research staff.
- For participants recruited from the Chapel Hill catchment area, the intervention will be delivered in person and by phone:
 - In person, face-to-face counseling visits, will be given at the UNC Center for Health Promotion and Disease Prevention, located at [name]. A minimum of 4 in-person counseling visits will be delivered at this location (first visit of Phase I, first visit of Phase II, 2 month follow-up visit of Phase II, and first visit of Phase III).
 - The other visits may be given in person or by phone. The phone counseling sessions may be supplemented with use of shared screen technology (e.g., Zoom™ session)

- The location of our counseling sessions in Eastern North Carolina is to be determined and will included in a further version of the protocol. (Enrollment visits in eastern North Carolina will start no later than April, 2021.)
- We will encourage participants to take part in all sessions. However, a participant will not be dropped from the study based on session participation. In the extreme, we will invite participants back for measurement visit even if they did not participate in any intervention counseling sessions.
- If a participant takes part in 70% or more of anticipated visits, we will consider this a “full-dose.”
- The intervention format for this study is individual; there will be no group sessions or activities.

Description of Intervention for Phase 1

Phase I – Lifestyle Intervention: The content for this phase is currently available at:

<http://hpdp.unc.edu/research/medsouth/med-south-materials/>. As outlined below under Phase I modifications, we will adapt the current physical activity intervention so that 1) it is less intensive than previously tested by our group and 2) approximates what we anticipate to be the physical activity recommendations in the augmented control group. Our goal in doing so is to isolate the dietary pattern as the primary behavioral intervention evaluated in this study.

Session Content and Delivery: The following content is addressed during the 4 major counseling session:

- Session 1: Nuts, Dressings, and Oils
- Session 2: Vegetables, Fruit, Whole Grains, and Beans.
- Session 3: Drinks, Desserts, Snacks, Eating Out, and Salt
- Session 4: Fish, Meat, Poultry, Dairy, and Eggs

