6.2 FIDELITY

6.2.1 INTERVENTIONIST TRAINING AND TRACKING

We will assess fidelity in intervention delivery as follows:

- Enhanced usual care (WW™):
 - Per our data use agreement, WW™ has agreed to provide the study with the following process data: number of workshops attended (including dates of visits), workshop weights (if available), number of website or phone app logins (including dates and duration if available), and participant reported dietary and physical activity data.
 - At all study follow-up measurement visits (4, 12, and 24 months), research staff will carefully assess number, type, and duration of weight loss counseling sessions complete as part of the WW™ program.
- Med-South Weight Loss Program: We will assess fidelity of intervention delivery through multiple channels as describe below.
 - All counseling sessions will be logged into our REDCap data management program, including date and duration of visit.
 - After each visit, the counselor completes a checklist to indicate the components of counseling that were covered during the visit.
 - Audio recordings of up to 20% of sessions will be conducted during the 2-year period.
 - During Phase I and the early part of Phase II (first 2 months) a random 50% of the recorded counseling sessions will be reviewed and feedback provided to counselors. Recordings will be reviewed by study staff using a checklist to assess planned counseling components (accuracy of content covered and quality of delivery). If we find delivery fidelity is less than 80% of anticipated based on successful completion of counseling components, then the frequency of providing feedback to counselors from reviewed audio recordings will increase to ensure that the delivery fidelity goal has been achieved.
 - During the latter part of Phase II (last 6 months) and Phase III, audio recording will drop to 10% of visits (with review of up to 50% of recorded sessions), unless delivery fidelity is not achieved, in which the proportion reviewed will be increased to document achievement of fidelity goals.

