## **9.6 Sample Size Justification**

For our primary outcome, percent change in weight at 24 months, we have calculated sample size based on a two-sided test of significance with  $\alpha=0.05$  and the standard deviation (SD) of percent change in weight of 7.3% as observed in the Heart Health Lenoir Project. Table 5 illustrates sample size calculations (allowing for 20% attrition) for various differences in mean changes between study groups based on a 1:1 randomization allocation ratio. This table also provides power calculations to detect differences in weight change compared to augmented usual care separately for pre-specified subgroups (those with vs. without diabetes, female vs. male, and white vs. African American assuming no sub-group is less than 40% of the overall sample). We expect the intervention to reduce weight by at least 5% and that average weight loss in the intervention group will exceed that in augmented usual care by at least 4% (we estimate weight loss in usual care of  $\leq 1\%$ ). Our plan to enroll 360 participants provides excellent power for our primary outcome

(>99%) and reasonable power (82%) within each of our pre-specified sub-groups. For a difference between groups as small as 3%, we still have robust power for our primary outcome. Although we do not anticipate major differences in weight loss between those in our pre-specified subgroups, we will test the potential for large differential effects between subgroups using interaction terms. However, under the assumptions described above, our power to detect realistic difference in effects of 2-3% between these subgroups will be limited (about 20-40%). Also, for a difference in proportions of those losing  $\geq$  5% body weight as small as 15% (e.g., 15% control vs. 30% intervention), allowing for attrition, the proposed sample size provides 85% power. For several secondary outcomes, we present in Table 5 minimally detectable differences corresponding to effect size of 0.33 for the sample size of 360 with 20% attrition, 80% power, and  $\alpha = 0.05$ .

Note, the table below assume sample size of 350. After funding, the investigative team elected to increase sample size to 360 with a goal of 120 participants per wave.

| Table 5. Power Estimates for % Change in Weight at 24 Month Follow-up |                   |                                    |   |
|--|-------------------|------------------------------------|---|

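### The primary model and power figures make no allowance for Med-South participants sharing counsellors; if counsellors differ, the 24-month SE is too small for inference beyond those counsellors

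*SAP*

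**What the plan says.** **Delivery.** Protocol 6.1.2 has Med-South given by trained research staff and says: "The intervention format for this study is individual; there will be no group sessions or activities". SAP 6.5 counts 30 planned visits over 24 months (4, 14 and 12 by phase). Protocol 4.3 argues that individual delivery "provides the advantage of a closer relationship between participant and interventionist". SAP 5.2 describes WW as mainly a web-based app, with group sessions optional once WW reopened them.

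**Analysis.** SAP 9.4.1 fits a linear mixed model with fixed effects for group, visit, group-by-visit, site, baseline weight, race/ethnicity, gender and diabetes status; age was added later. The only correlation modelled is within a participant: "To account for within-participant correlation, the model will allow for correlated error terms using an unstructured covariance matrix". The 24-month contrast is used "to test for a treatment effect at 24-months at the 5% significance level". Site means the referring practice, as the study-sites note in that section shows.

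**Sample size.** SAP 9.6 uses a two-sided 5% test, 20% attrition and an SD for "percent change in weight of 7.3% as observed in the Heart Health Lenoir Project". It concludes: "For a difference between groups as small as 3%, we still have robust power for our primary outcome".

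**Not stated in either document.** The number of counsellors, their caseloads, whether a participant keeps one counsellor, a counsellor ICC, a counsellor term or cluster-robust variance, or a design effect.

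**The concern.** The arms differ in structure. Each Med-South participant is counselled by one of a finite set of staff; WW has no study counsellor. If some counsellors obtain more weight loss than others, participants who share a counsellor have correlated outcomes, and the Med-South mean is less precise than the count of participants suggests.

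Site cannot absorb this. Protocol 5.5 says research staff, not clinic staff, give the intervention, and Protocol 4.1 says one investigational team delivers it, so counsellors are not tied to practices by design.

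At stake is whether the primary result supports a claim about the Med-South programme in the hands of other counsellors. For that claim an ignored counsellor effect makes the interval too narrow, the type I error above 5%, and the stated power too high, most visibly at the 3-point difference.

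**Working it through.** **1. Inputs**
- Two-sided alpha 0.05: SAP 9.6, "we have calculated sample size based on a two-sided test of significance with" alpha 0.05.
- SD 7.3 points, 20% attrition, 1:1 allocation: SAP 9.6.
- Analysed per arm: 360 × 0.8 / 2 = 144; for the power table, 350 × 0.8 / 2 = 140.
- Number of counsellors *k* (4, 8 or 12, equal caseloads) and ICC (0.01 to 0.05): **assumptions**; neither is in the documents.

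**2. The plan's own figures**

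A two-sample t-test power calculation with independent participants, at 350 enrolled:

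| Difference | Overall (140 per arm) | Plan | Subgroup (56 per arm) | Plan |
|---|---|---|---|---|
| 3 points | 0.929 | 0.93 | 0.578 | 0.58 |
| 4 points | 0.996 | 99.5% (protocol), 0.99 (SAP) | 0.820 | 0.82 |

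The cells for 300 and 400 enrolled also agree. The table is therefore a calculation for independent participants, with no allowance for clustering.

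**3. Clustering in Med-South only**
- Design effect: DE = 1 + (144/k − 1) × ICC
- SE assuming independence: 7.3 × √(2/144) = 0.860
- True SE: 7.3 × √((1 + DE)/144); SE ratio r = √((1 + DE)/2)
- Actual error of the planned test: 2 × (1 − Φ(1.96/r))
- Power: noncentral t with the true SE and Satterthwaite df, where df = (v1 + v0)² / (v1²/(k − 1) + v0²/143), v1 = 7.3² × DE/144 and v0 = 7.3²/144

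Worked case, k = 4 and ICC 0.05: DE = 1 + 35 × 0.05 = 2.75; r = √(3.75/2) = 1.37; SE = 7.3 × √(3.75/144) = 1.178; error = 2 × (1 − Φ(1.96/1.369)) = 15.2%; df = 5.6.

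| k | ICC | SE ratio | Type I error of planned test | Power, 3 points | Power, 4 points |
|---|---|---|---|---|---|
| 12 | 0.01 | 1.03 | 5.6% | 91% | 99% |
| 8 | 0.01 | 1.04 | 6.0% | 89% | 99% |
| 8 | 0.03 | 1.12 | 8.0% | 84% | 98% |
| 8 | 0.05 | 1.19 | 10.1% | 78% | 95.5% |
| 4 | 0.01 | 1.08 | 7.1% | 82% | 97% |
| 4 | 0.03 | 1.24 | 11.2% | 67% | 89% |
| 4 | 0.05 | 1.37 | 15.2% | 56% | 79% |

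Without clustering, 144 per arm gives about 94% power at 3 points and 99.6% at 4.

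**4. Simulation check.** Over 20,000 runs per setting, a t-test that ignores counsellors rejected a true null in 5.0% (ICC 0), 7.4% (k = 4, ICC 0.01), 15.4% (k = 4, ICC 0.05) and 9.9% (k = 8, ICC 0.05).

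**5. Interval width.** With 4 counsellors the t critical value is 2.26 at ICC 0.01 and 2.49 at ICC 0.05. Relative width is 1.084 × 2.26/1.96 = 1.25 and 1.369 × 2.49/1.96 = 1.74.

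These are two-sample approximations at 24 months; they leave out covariate adjustment and the earlier visits.

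**The case against.** **The inputs that set the size are unknown.** A reader might infer that a small pool of counsellors is documented, or that the true error rate is about 15%. Neither is supported. Protocol 6.1.2 says only trained research staff, and the 15.2% needs both 4 counsellors and ICC 0.05. With 12 counsellors and ICC 0.01 the effect nearly vanishes. This stands, and it limits the point to a conditional one.

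**Counsellors may not differ much.** Calling the relationship an advantage does not show that counsellors vary. Protocol 6.2.1 provides recorded sessions, feedback, and more feedback if fidelity falls below 80%; Protocol 6.1.2 describes standard session content. These controls may lower the ICC, but they neither estimate it nor put it in the model.

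**Contact and assignment may be looser than a simple nested structure.** Thirty visits is the plan, not attendance: the Phase III description in Protocol 6.1.2 makes monthly calls as needed. Switching counsellors would dilute clustering and make a single main counsellor an approximation. Optional WW groups could create some clustering in that arm, which would not remove the problem in Med-South. All of this affects size.

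**The inference target may be narrow.** Protocol 4.2 calls the trial explanatory. For the effect as delivered by these counsellors, the planned SE is roughly right, and that is a defensible target. The SAP does not say it is the intended one, and the title and rationale of the protocol look towards use in primary care practices.

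**Feasibility and timing.** Protocol 6.2.1 names date and duration among the logged session data, and says "After each visit, the counselor completes a checklist to indicate the components of counseling that were covered during the visit"; it does not say that counsellor identity is stored. SAP 9.4.1 records a May 2025 review and final models with age, so the primary model has apparently been run. Both limits carry into the fix.

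**Conclusion.** The gap is real: the primary model and power figures assume no correlation among participants who share a counsellor, in a design where only one arm has counsellors. Any positive counsellor ICC makes the planned 24-month SE and p-value too small for inference beyond the particular counsellors; conditional on them, the planned SE is about right.

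The size cannot be established from the documents. At 144 per arm, SD 7.3 and equal stable caseloads, the type I error runs from about 5.6% (12 counsellors, ICC 0.01) through 6.0% to 10.1% (8 counsellors, ICC 0.01 to 0.05) to 7.1% to 15.2% (4 counsellors, same ICCs).

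A reader might also infer that the trial is underpowered for its planned 4-point difference, or, conversely, that power there is safe whatever the clustering. Neither follows. Power at 4 points stays at 95% or more with 8 counsellors, but with 4 counsellors and small-sample degrees of freedom it is 97%, 89% and 79% at ICC 0.01, 0.03 and 0.05. The claim of robust power at 3 points is the more fragile one. None of this invalidates the primary analysis; it calls for a sensitivity analysis and fuller reporting.

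**What to change.** 1. **SAP 9.4.1:** keep the primary analysis unchanged. If counsellor identity can be recovered from the session records, add a sensitivity analysis of the same 24-month contrast with a counsellor random effect in Med-South only, each WW participant as a singleton, and Satterthwaite or Kenward-Roger degrees of freedom. State how a participant with more than one counsellor is assigned. Label the analysis post hoc if the primary model has already been run.
2. **Reporting:** give the number of counsellors, caseloads, any switching and the estimated ICC. If identity cannot be recovered, say so and limit the inference to the counsellors used.
3. **SAP 9.6:** state that the power figures assume no counsellor clustering.

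**Cost:** SAP wording, one extra model, and a check of the session records. No new data collection is needed if identity was recorded. The downside is statistical: with few counsellors the variance component is imprecise and the interval could be much wider, about 1.25 to 1.74 times the planned width with 4 counsellors at ICC 0.01 to 0.05.

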9.4.2 ANALYSIS OF THE PRIMARY ENDPOINT(S)

The primary analysis will be conducted using the ITT Population and will be repeated secondarily using the Per Protocol Population.

Percent change in body weight = (Follow-up weight – baseline weight)/baseline weight x 100. We will compare the longitudinal mean % change in body weight between groups using analysis of covariance (ANCOVA), conducted using a linear mixed model. A mixed model will allow for the inclusion of all observed follow-up data for all participants. The model will include fixed effects for group, follow-up visit (4, 12, or 24 months), group-by-visit interactions, site, baseline weight, race/ethnicity, sex, and diabetes status. To account for within-participant correlation, the model will allow for correlated error terms using an unstructured covariance matrix. For the primary comparison, we will use an appropriately specified linear contrast of the model parameters to test for a treatment effect at 24-months at the 5% significance level. Secondarily, we will compare the groups at other time points and will estimate effect sizes along with 95% confidence intervals for each comparison. Secondarily, we will expand the model by including appropriate interaction terms, one at a time, to examine the potential heterogeneity of intervention effect in sub-groups, including diagnosis (diabetes vs. no diabetes), race/ethnicity, sex, and by degree of baseline obesity (BMI > 40 vs. less). Interaction terms will be tested at the 5% significance level.

We will use a longitudinal mixed effects logistic regression model to compare the groups for proportions losing > 5% body weight at each follow-up visit; estimates of odds ratios and 95% confidence intervals will be provided. This model will control for the same covariates specified for the primary model.

Missing Data

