### Randomization and Blinding

This is a single-site (per NIH definition) open-label randomized controlled trial enrolling 360 participants for 7 local practices desiring weight loss and followed over 24 months. Participants were enrolled in 3 sequential waves as described below. Participants were randomized in 1:1 ratio. Statistician will be blinded for the primary analyses.

Group 1: Med-South Weight Loss Program (the intervention)

Group 2: Weight Watchers (WW™) (augmented usual care)

Randomized assignment were done by a computer program stratifying on Wave and diabetes status and using randomly permuted blocks of random sizes (4 and 6) to achieve balance in the participants' allocation.

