## **5.2                   Planned Enrollment**

The overall sample size is 360. The study plan was to conduct contemporaneous enrollment of sub-groups to ensure that at least 40% of participants will be African American, diagnosed with diabetes, and male. At the initial study practice, the UNC General Internal Medicine practice, the contemporaneous enrollment protocol was followed for the enrollment of approximately ½ the sample, after which there were not sufficient potential participants in sub-groups of interest to continue this protocol. Instead, complete sampling was done of specific of subgroups of interest (e.g. African American men).

Enrollment was conducted in 3 sequential waves. Wave 1 included the large UNC General Internal Medicine practice located in Chapel Hill, NC. Wave 2 included two internal medicine practices in Chapel Hill, NC (Chapel Hill Internal Medicine and UNC Internal Medicine at Weaver Crossing) and one family medicine practice in Hillsborough, NC (Orange Family Medicine Group). Wave 3 included two family medicine practices in Durham, NC (UNC Family Medicine Center at Durham and UNC Family Medicine at Southpoint) and one internal medicine and pediatrics practice located near Chapel Hill, NC (North Chatham Pediatrics & Internal Medicine). Study enrollment and measurement visits were conducted at the Center for Health Promotion and Disease Prevention, located at [name]. For the Med-South intervention group, the first counseling session was conducted in person with the large majority of follow-up visits conducted by phone. For the WW group, the intervention was primarily given via web-based app for use on personal computers, tablets, or smart phones. WW participants had the option to attend group sessions once these were offered by WW after closure due to the Covid 19 pandemic.

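### SAP 9.4.1 replaces the protocol's BMI > 40 subgroup with an unexplained sample-median split; either split loses information that a continuous BMI-by-group interaction would keep

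*SAP*

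**What the plan says.** Protocol 9.4.2 adds interaction terms to the primary mixed model one at a time. One of them is "by degree of baseline obesity (BMI > 40 vs. less". SAP 9.4.1 keeps that structure but defines the term "by degree of baseline obesity ( $BMI \geq \text{median}$ vs. less". In both documents the term stands beside diabetes, race/ethnicity and sex.

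On the tests themselves, SAP 9.4.1 says: "Interaction terms will be tested at the 5% significance level". It then carries the same interaction terms into the logistic model for losing at least 5% of baseline weight, so the BMI cut governs subgroup results for both weight endpoints.

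Neither document gives the median, the distribution of baseline BMI or the share of participants above 40. The SAP gives no reason for the new cut, although it does explain its revised visit windows (5.4), its pooling of two practices (9.4.1, study sites) and its merging of two censoring analyses (6.4).

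BMI is not one of the three named subgroups, which Protocol 9.4.7 lists as diabetes, race and sex. The SAP dates its draft 9/10/24, after randomisation was complete and before outcomes were analysed.

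**The concern.** There are two problems, both modest.

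The first is an unexplained disagreement between the two plans on a planned test. A fixed threshold of 40 is set in advance and can be applied in any other study. A sample median depends on who enrolled, and its value is known only once the sample is complete.

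The second is common to both plans. A two-group split treats people just either side of the cut as different, and people far apart on the same side as alike. Height and weight are measured on everyone at baseline, so the discarded detail is already in the data. Interaction tests in a trial of this size have little power to spare.

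At stake is the readability and sensitivity of one secondary heterogeneity test, for percent weight change and for the 5% responder model. The 24-month primary contrast is not involved.

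**Working it through.** **Inputs from the documents**
- Standard deviation (SAP 9.6): "the standard deviation (SD) of percent change in weight of 7.3", in percentage points.
- Dropout (SAP 9.6): "allowing for 20% attrition".
- Allocation (SAP 5.1): "Participants were randomized in 1:1 ratio".
- Sample size (SAP 5.2): "The overall sample size is 360"; the power table in SAP 9.6 was computed at 350.
- Level: 5% for interactions (SAP 9.4.1), taken as two-sided because SAP 9.6 says "we have calculated sample size based on a two-sided test of significance".

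**Assumed, because the documents do not give it:** the distribution of baseline BMI. Entry requires BMI of at least 30 in the health record, with a recheck floor of 27.5, so exact normality is doubtful. I therefore used several shapes.

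**1. Reproduce the plan's own interaction power.** With n completers, a share p in one subgroup and a difference d between the two subgroup effects:

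SE = 2 × SD / √(n p (1−p)); power = Φ(d/SE − 1.96).

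At N = 350, n = 0.8 × 350 = 280. With p = 0.4, SE = 14.6/√67.2 = 1.78, and power is 20.1% for d = 2 and 39.1% for d = 3. With p = 0.5, SE = 1.745, and power is 20.8% and 40.5%. This matches the stated 20-40%, which the plan gives for its three named two-group factors and not for BMI.

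**2. Median split at the enrolled size.** At N = 360, n = 288. With p = 0.5, SE = 14.6/√72 = 1.721, and power is 21% (d = 2) and 41% (d = 3).

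**3. Information kept by a cut.** For a linear interaction, the information that a two-group test keeps, relative to continuous BMI, is the squared correlation between BMI and the cut indicator. For normal BMI with a share p above the cut at z, this is φ(z)²/(p(1−p)). At the median it is 0.3989²/0.25 = 2/π = 0.637, a loss of 36.3%.

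For the BMI > 40 cut under the same normal assumption:

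| Share above 40 (assumed) | Kept | Lost |
|---|---|---|
| 40% | 0.622 | 38% |
| 30% | 0.576 | 42% |
| 20% | 0.490 | 51% |
| 10% | 0.342 | 66% |

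For other assumed shapes, by simulation:

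| BMI shape | Median split loses | BMI > 40 loses |
|---|---|---|
| Normal, truncated at 27.5 or 30 | 34-36% | 33-41% |
| Lognormal, truncated at 27.5 or 30 | 38-43% | 34-37% |
| 30 plus exponential | 52% | 35-38% |

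Under normality the BMI > 40 cut loses more than the median; under the right-skewed shapes it loses less.

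**4. Power with continuous BMI.** Under a linear interaction, d/SE for the split equals the continuous-BMI value multiplied by the square root of the information kept. Using 0.637, whose square root is 0.798:
- d = 2: 2/1.721 = 1.162; 1.162/0.798 = 1.457; Φ(1.457 − 1.96) = 31%.
- d = 3: 3/1.721 = 1.743; 1.743/0.798 = 2.185; Φ(2.185 − 1.96) = 59%.

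Over the full range of median-split losses, 34% to 52%, the square roots are 0.812 and 0.693. Power is then 30-39% for d = 2 and 57-71% for d = 3. Here d is the difference in effect between the two halves of the sample.

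**The case against.** The strongest defence is that the change may have improved the test. For a given difference between the two groups, an even split is the most precise: at N = 360 the SE is 1.72 at 50:50, 1.88 at 30:70 and 2.15 at 20:80, and power for 3 points is 41%, 36% and 29%. Under normality the median also keeps more information than BMI > 40. This stands, so the SAP's cut is not worse than the protocol's on efficiency grounds.

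Four stronger readings are tempting, and the documents do not support them.

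- **The change of cut cost 36%.** That figure compares a median split with continuous BMI, which neither plan proposed. The protocol's cut dichotomises too.
- **The cut was picked from the results.** The SAP dates itself before outcome analysis, and a median is a mechanical rule using baseline data only. The SAP does contain later dated edits (10/28/24, 4/19/25, May 2025), and the BMI wording has no date of its own, but a missing date is not evidence of an outcome-driven choice.
- **The plan's 20-40% is BMI power that the split then erodes.** It describes the three named two-group factors and is already a two-group figure.
- **A median cut means nothing outside this sample.** Its value can be reported. It is only not fixed in advance, as 40 is.

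The gain from continuous BMI also depends on a roughly linear interaction; a true threshold effect would change the comparison. And the gain still leaves the test short of conventional power.

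**Conclusion.** The point holds as a minor but worthwhile correction. The two plans disagree on the BMI cut, no reason or median value is given, and both dichotomise a variable measured on everyone. Against a continuous, linear BMI-by-group interaction, a median split loses about 36% of the information if BMI is roughly normal, and 34-52% over the shapes tried. The BMI > 40 cut loses 33-66% over the shapes and shares tried; which cut is worse depends on a BMI distribution that the documents do not give. In power terms the contrast is about 21% against 31% for 2 points, and 41% against 59% for 3 points.

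These figures rest on the plan's SD of 7.3, 20% attrition, N = 360, a two-sided 5% level and linearity, with no allowance for covariate adjustment. The test is secondary and outside the three named subgroups. The primary 24-month comparison is untouched.

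**What to change.** In SAP 9.4.1:
- Test the group-by-baseline-BMI interaction at 24 months with BMI continuous: linear, with a spline check for non-linearity. Do this for both percent weight change and the 5% weight-loss model.
- Report the estimated treatment effect with its 95% interval at fixed BMI values, for example 30, 35, 40 and 45.
- Keep the protocol's BMI > 40 split as a supporting display.
- If the median split is retained, report the median and add a dated sentence explaining why it replaced 40.

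The cost is a few sentences and some programming, with no new data and no loss of sample. There are two small downsides. The linear term carries an assumption, which the spline check addresses. Also, the SAP records a review of the analysis in May 2025, so if the continuous test is added after outcomes were analysed, it must be labelled post hoc.
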